### 9.2.3. Adverse Event Summaries

Overall summaries of TEAEs by treatment regimen will be provided during the INCB050465 initial QD dosing period, maintenance dosing period, and overall period (ie. all TEAEs regardless of the timing of occurrence). These summaries will include the following:

- Number (%) of participants reporting any TEAEs
- Number (%) of participants reporting any Grade 3 or higher TEAEs
- Number (%) of participants reporting any serious TEAEs
- Number (%) of participants reporting any TEAEs related to INCB050465
- Number (%) of participants reporting any Grade 3 or higher TEAEs related to INCB050465
- Number (%) of participants reporting any serious TEAEs related to INCB050465

- Number (%) of participants who had TEAE with fatal outcome
- Number (%) of participants with INCB050465 dose reductions because of TEAEs
- Number (%) of participants who temporarily interrupted INCB050465 because of TEAEs
- Number (%) of participants who permanently discontinued INCB050465 because of TEAEs

The following summaries will be produced for TEAEs during the overall period by MedDRA term (if 10 or fewer participants appear in a table, a listing may be appropriate):

- Summary of TEAEs by SOC and PT
- Summary of TEAEs by PT in decreasing order of frequency
- Summary of TEAEs by SOC, PT, and maximum severity
- Summary of TEAEs by PT and maximum severity in decreasing order of frequency
- Summary of Grade 3 or higher TEAEs by SOC and PT
- Summary of Grade 3 or higher TEAEs by PT in decreasing order of frequency
- Summary of serious TEAEs by SOC and PT
- Summary of serious TEAEs by PT in descending order of frequency
- Summary of INCB050465 treatment-related TEAEs by SOC and PT
- Summary of INCB050465 treatment-related TEAEs by PT in decreasing order of frequency
- Summary of INCB050465 treatment-related TEAEs by SOC, PT, and maximum severity
- Summary of Grade 3 or higher INCB050465 treatment-related TEAEs by SOC and PT
- Summary of INCB050465 treatment-related serious TEAEs by SOC and PT
- Summary of TEAEs with a fatal outcome by SOC and PT
- Summary of TEAEs leading to INCB050465 dose reduction by SOC and PT
- Summary of TEAEs leading to INCB050465 dose interruption by SOC and PT
- Summary of TEAEs leading to discontinuation of INCB050465 by SOC and PT
- Summary of selected TEAEs of special interest by maximum severity

- Summary of time to onset of selected TEAEs of special interest
- Summary of time to onset of selected TEAEs of special interest: life-table method
- Summary of longest duration of selected TEAEs of special interest

The following supporting summaries will be produced for TEAEs during the INCB050465 initial QD dosing period and the maintenance dosing period by MedDRA term. For the supporting summaries during the maintenance dosing period, participants who cross over to the selected treatment regimen after the start of the maintenance dosing period will be summarized in a separate group (ie, Crossover).

- Summary of TEAEs by PT in decreasing order of frequency
- Summary of TEAEs by PT and maximum severity in decreasing order of frequency
- Summary of Grade 3 or higher TEAEs by PT in decreasing order of frequency
- Summary of serious TEAEs by PT in descending order of frequency
- Summary of TEAEs with a fatal outcome by SOC and PT
- Summary of TEAEs leading to discontinuation of INCB050465 by SOC and PT

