Study Schedule/Procedures: Subjects will undergo screening assessments, including physical examination; laboratory tests, including pregnancy and serology tests; an ECG; and a bone marrow examination to determine eligibility. During the treatment period, subjects will be monitored for safety through disease-specific physical examinations, including vital signs, ECOG performance status, assessment of AEs, ECGs, and laboratory assessments every 4 weeks through Week 48 and then every 12 weeks thereafter; hematology will be assessed every 2 weeks for the first 8 weeks. Disease status will be assessed (using the same modality [CT/MRI] from screening) every 8 weeks through Week 24, then every 12 weeks through Week 96, and then every 24 weeks thereafter until disease progression.

[REDACTED] Subjects withdrawn from study treatment for reasons other than disease progression will be followed for disease status until either radiologic disease progression, the start of a new anticancer therapy, consent withdrawal, or death (whichever occurs first). After permanently discontinuing study treatment, subjects will be followed every 12 weeks for subsequent anticancer therapies and survival.

Estimated Duration of Participation: Subject participation from screening through follow-up is expected to average approximately 25 months, which includes the following:

- A screening period lasting up to 28 days.
- A treatment period lasting as long as the subject is receiving benefit, tolerating the regimen, and has not met withdrawal criteria (approximately 52 weeks).

- A safety follow-up period lasting 30 to 35 days.
- A disease and survival follow-up period until the end of the study.

At the end of the study, subjects who have completed at least 24 months of study participation (starting from first dose of INCB050465), who remain on active study treatment, and who have no evidence of progressive disease will have the option to continue on monotherapy with INCB050465 provided within a rollover Protocol, as local law permits.

Estimated Number of Subjects: Approximately 90 subjects who have not received prior BTK inhibitor will be enrolled into Cohort 2. Cohort 1, which comprises subjects who have received prior ibrutinib, will be closed to further enrollment with Protocol Amendment (Version) 3.

Principal Coordinating Investigators:

US: [REDACTED], MD, [REDACTED], MI, USA

EU: [REDACTED], MD, [REDACTED], United Kingdom

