1.5. Potential Risks and Benefits of the Treatment Regimen

INCB050465 has effects on the immune system. Therefore, subjects in this study will be monitored closely for evidence of infections or new cancers, and study treatment administration will be discontinued if there is evidence of clinically significant infection or new cancer.

While PJP has not been reported with the use of INCB050465 either as monotherapy or in combination therapy, subjects who receive INCB050465 in this study will receive PJP prophylaxis. Subjects will be asked to report all sulfa drug allergies and those allergic to standard PJP prophylaxis with sulfonamide antibiotics will receive either inhaled pentamidine or atovaquone for PJP prophylaxis; these subjects will not be given dapsone.

As presented in Section 1.3, the most common AEs ($\geq 20\%$) observed with INCB050465 monotherapy have been nausea, diarrhea, fatigue, cough, rash, and vomiting. Serious AEs (≥ 2 subjects) have included colitis, diarrhea, sepsis, hypotension, ventricular tachycardia, pyrexia, respiratory failure, pneumonia, bronchitis, exfoliative dermatitis, syncope, urinary tract infection, and bacteremia. Dose modification guidance and supportive care guidelines for diarrhea/colitis are implemented in this study.

Based on efficacy and safety data from the ongoing Study INCB 50465-101, which evaluated a continuous 20 mg QD dose regimen, the treatment regimen for Study INCB 50465-204 will be 20 mg QD for 8 weeks, followed by either 20 mg once weekly or 2.5 mg QD of INCB050465. As detailed in Section 1.3, these regimens are proposed to assess whether the frequency of AEs leading to treatment withdrawal will be reduced while maintaining PI3K pathway inhibition and maintenance of response.

INCB050465 is metabolized primarily by CYP3A4; therefore, use of any potent CYP3A4 inhibitors or inducers within 14 days or 5 half-lives (whichever is longer) before the first dose of INCB050465 will be prohibited.

The effects of INCB050465 on fetal development has not been evaluated nor is it known whether INCB050465 passes into human breast milk; therefore, subjects who are pregnant or breastfeeding are excluded from participation in this study.

There are no preclinical data available to date on the potential phototoxicity of INCB050465. Therefore, subjects enrolled in this study taking INCB050465 will be instructed by the site staff

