• Any recurrent Grade 3 toxicity after 2 dose reductions.	Discontinue INCB050465 administration and follow-up per Protocol. Exceptions require approval of sponsor.
• Any other Grade 4 toxicity.	Discontinue INCB050465 administration and follow-up per Protocol. Exceptions require approval of sponsor.

ALT = alanine aminotransferase; AST = aspartate aminotransferase; CMV = cytomegalovirus; IV = intravenous; ULN = upper limit of normal.

Table 4: Dose Levels and Reductions for INCB050465

Timepoint	Treatment A	Treatment B
Starting dose	20 mg QD for 8 weeks (Day 1 through Day 56)	20 mg QD for 8 weeks (Day 1 through Day 56)
First dose reduction	10 mg QD	10 mg QD
Second dose reduction	5 mg QD	5 mg QD
Week 9 (Day 57) onward	20 mg once weekly ^a	2.5 mg QD ^b
First dose reduction	10 mg once weekly	1 mg QD ^c
Second dose reduction	5 mg once weekly	NA

^a All subjects will receive 20 mg once weekly at Week 9 (Day 57) regardless of prior dose level, unless a dose modification of a switch to a QW schedule before Week 9 is required for diarrhea/colitis management (see Table 5).

^b All subjects will receive 2.5 mg QD at Week 9 (Day 57) regardless of prior dose level, unless a dose modification of a switch to a QW schedule is required for diarrhea/colitis management (see Table 5).

^c Further dose modification due to diarrhea or colitis for subjects on 1 mg QD is permitted (see Table 5).

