### **5.2. Treatment Groups**

This is a Phase 2, open-label study. All analyses will be conducted independently for Cohort 1 and Cohort 2, and there will not be multiplicity adjustment between the cohorts. Within each cohort, there will not be any statistical comparison between the treatment groups.

For the purpose of analysis, the 20 mg QW dosing period in Treatment A and the 2.5 mg QD dosing period in Treatment B are considered maintenance dosing periods. Within each cohort, data will be presented in summary tables by actual received treatment regimen and combined, with an exception for participants who cross over to the selected treatment regimen after the start of the maintenance dosing period.

For participants who cross over from the initially assigned treatment regimen to the selected treatment regimen, if the crossover happens before/on the start of the maintenance dosing period, then the participant will be summarized, according to the actual received treatment, in the selected treatment regimen; otherwise, the participant will be summarized in:

- A separate treatment regimen (ie, Crossover) for the safety summaries during the maintenance dosing period (eg. summaries of TEAEs and exposure).
- The initially assigned treatment regimen for all other summaries.

Per Protocol Amendment (Version) 3, Cohort 1 was closed to further enrollment. If the number of participants who have enrolled in Cohort 1 is relatively few, summary tables will be replaced with listings.

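### Period-specific TEAE tables give crude percentages over 8 weeks and over an open-ended maintenance period, so they cannot show whether AE withdrawals became less frequent

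*SAP*

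**What the plan says.** SAP 9.2.3 sets the reporting periods: "Overall summaries of TEAEs by treatment regimen will be provided during the INCB050465 initial QD dosing period, maintenance dosing period, and overall period". The entries are counts with percentages, for example "Number (%) of participants who permanently discontinued INCB050465 because of TEAEs". A second set follows: "The following supporting summaries will be produced for TEAEs during the INCB050465 initial QD dosing period and the maintenance dosing period by MedDRA term". That set includes "Summary of TEAEs leading to discontinuation of INCB050465 by SOC and PT". No entry uses participant-time, and the denominator for the maintenance columns is not stated.

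The two periods differ in length by design. Protocol Table 4 gives the start of both regimens as "20 mg QD for 8 weeks (Day 1 through Day 56"). SAP 5.2 defines the rest: "the 20 mg QW dosing period in Treatment A and the 2.5 mg QD dosing period in Treatment B are considered maintenance dosing periods". Maintenance has no planned end. The Protocol synopsis describes the treatment period as lasting while the subject is benefiting, "tolerating the regimen, and has not met withdrawal criteria (approximately 52 weeks").

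Protocol 1.5 gives the purpose: "these regimens are proposed to assess whether the frequency of AEs leading to treatment withdrawal will be reduced".

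**The concern.** A crude percentage accumulates with time at risk. A lower event rate over a longer period can therefore produce a higher percentage than a higher rate over 8 weeks. The reduction that the regimens were designed to look for could be hidden in the tables where a reader would look for it.

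Regimen columns can differ in follow-up too. The 30 additional participants join the selected regimen only after the first 60 have enrolled, so that column includes later entrants. Under SAP 5.2, participants who switch after maintenance has started leave their own regimen's maintenance safety column for a Crossover group. They were still on treatment when they switched. The non-selected column thus loses time free of AE withdrawal but keeps those who withdrew earlier, so its crude percentage can rise for that reason alone.

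At stake is the description of how tolerable the maintenance dose is. The primary efficacy analysis is not affected.

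**Working it through.** The documents give no expected figure for these tables, so the size has to be illustrated.

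**Inputs**
- Initial period: 8 weeks (Protocol Table 4).
- Total treatment: about 52 weeks (Protocol synopsis), so maintenance is 52 − 8 = 44 weeks.
- AE discontinuation in the Phase 1/2 study: 14 of 72, median treatment 122.5 days (Protocol 1.3). The stated 19% reproduces: 14/72 = 19.4%. 122.5/7 = 17.5 weeks.
- Assumptions: constant hazard within each period; the median taken as common exposure; maintenance hazard half the initial one (the documents state no target).

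**Base case, maintenance entrants as denominator**
- Hazard: h = −ln(1 − 14/72)/17.5 = 0.01236 per week.
- Initial: 1 − exp(−8h) = 9.4%.
- Maintenance: 1 − exp(−44 × h/2) = 23.8%.
- Crude ratio: 23.8/9.4 = 2.53, although the hazard ratio is 0.50.
- As rates: about 64 and 32 per 100 participant-years, or 64/12 = 5.4 and 32/12 = 2.7 per 100 participant-months. The halving is visible.

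**Reference points at 8 + 44 weeks**
- With no change in hazard the crude ratio would be 4.46.
- The percentages become equal only when the maintenance hazard falls to 8/44 = 18% of the initial one.

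**Sensitivity to duration and denominator (hazard halved)**

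| Total weeks | Initial | Maintenance | Ratio, entrants | Ratio, all treated |
|---|---|---|---|---|
| 26 | 9.4% | 10.5% | 1.12 | 1.01 |
| 39 | 9.4% | 17.4% | 1.85 | 1.68 |
| 52 | 9.4% | 23.8% | 2.53 | 2.29 |
| 104 | 9.4% | 44.7% | 4.75 | 4.31 |

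The all-treated ratio is the entrants' ratio multiplied by the share still at risk at week 8, 1 − 0.094. At 26 weeks it runs from 0.91 to 1.13 over the base rates tried.

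**Sensitivity to the base rate (52 weeks, entrants)**
- 35% over 17.5 weeks (the responder figure in Protocol 1.4; its exposure is not given, so 17.5 weeks is assumed): 2.34.
- 14/72 over an exponential mean exposure of 17.5/ln 2 = 25.2 weeks: 2.61.
- Rare-event limit, 0.5 × 44/8: 2.75.

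**Competing exits (52-week cap)**
With an assumed hazard g per week for other exits, each percentage becomes k/(k + g) × [1 − exp(−(k + g)t)], where k is the AE-withdrawal hazard in that period and t its length.
- g = 0.005: 9.2% and 21.5%, ratio 2.33.
- g = 0.03: 8.4% and 13.6%, ratio 1.62.

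**What the SAP already provides**
- SAP 6.4 summarises duration of treatment by period (Tables 3.1.2 and 3.1.3) but does not use it as a denominator for AEs.
- SAP 9.2.2 gives life-table onset analyses for the AEs of special interest, and 9.3.4 for Grade 3 or 4 ALT, AST and neutrophil events. All run from first dose.
- None of these covers AE discontinuation, serious TEAEs or TEAEs overall. Appendix A lists no exposure-adjusted AE table.

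**The case against.** The strongest reply is that the documents never commit to comparing weeks 1 to 8 with maintenance. Protocol 1.5 sets the regimens against the continuous 20 mg QD regimen of the Phase 1/2 study. The natural comparator is continued QD dosing after week 8, which neither planned regimen includes. Protocol 4.2 rules out comparisons between subjects or with historical controls, SAP 3.2 and 5.2 rule out statistical comparison of regimens, and SAP 11.2 calls the period tables supportive. This stands: the contrast between periods is a reading that the tables invite, not a planned analysis.

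The constant hazard is also doubtful. Protocol 5.4.4 says that most immune-related AEs arise after the first 9 weeks. Suppose, purely as an assumption, that the hazard under continuous QD would triple after week 8 and maintenance halves it. The rate ratio is then 3 × 0.5 = 1.5, so a rate would mislead as well. Those who reach week 9 are also a selected group. This too stands, and it limits what rates can show.

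The existing coverage is substantial. All 12 AEs of special interest have a life-table onset analysis at some grade, and a reader can look at onset before and after week 8. Of the 14 discontinuation events listed in Protocol 1.3, 10 are of those types (diarrhea 3, exfoliative dermatitis 2, colitis 2, and pneumonitis, rash and CMV colitis 1 each). Neutropenia makes 11. But onset is not discontinuation, and rash is analysed only at Grade 3 or higher.

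The reply that the tables are only descriptive does not remove the point. The dependence on time at risk is in the descriptive percentage itself.

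**Conclusion.** The gap is real and modest. AE discontinuation, serious TEAEs and Grade 3 or higher TEAEs are reported over unequal periods with no allowance for time at risk, and nothing else in the SAP supplies it for these categories. The crude percentages cannot show whether AE withdrawals became less frequent.

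The ratio of about 2.5 is illustrative. It needs a constant hazard, pools QD doses from 5 to 45 mg (34 of the 72 subjects at 20 mg), and gives every participant 44 weeks of maintenance. It runs from about 1 at 26 weeks of total treatment to about 4.75 at 104, and is 1.6 to 2.3 at 52 weeks with the competing exits assumed. Even a ratio near 1 would conceal a halved hazard.

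A reader might infer that a better maintenance dose would look 2.5 times worse, or that the trial will answer its own question with the wrong sign. The documents support neither. They fix no maintenance duration or denominator, they plan no contrast between periods, and their own remark on late-onset immune-related AEs undercuts the constant hazard.

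**What to change.** Keep the crude counts and amend SAP 9.2.3 as follows.

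1. In the overall period-specific TEAE summary, define the maintenance denominator as participants with at least one maintenance dose.
2. In the same summary, add participant-time in the period and the first-event rate per 100 participant-months with an exact 95% CI, for discontinuation due to TEAE, serious TEAEs and Grade 3 or higher TEAEs. The preferred-term tables do not need this.
3. Add one table of the cumulative incidence of discontinuation due to TEAE by regimen, from first dose and from first maintenance dose, for example at 6 and 12 months. Treat discontinuation for progression, death or other reasons as competing events, and censor at regimen switch so that time before the switch stays with the regimen received.
4. State that the contrast between initial and maintenance periods is descriptive, because rates remove neither the late onset of immune-related AEs (Protocol 5.4.4) nor the selection of participants who reach week 9.

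The dosing, AE and disposition data are already collected and listed. The cost is modest extra programming and imprecise rates in the small columns, such as Crossover. No trial procedure changes.

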### **9.3. Clinical Laboratory Tests**

#### **9.3.1. Laboratory Value Definitions**

Laboratory values and change from baseline values will be summarized descriptively by visit. Baseline will be determined according to Section 4.1.3. If there are multiple values that meet the criteria for baseline, the value from the central laboratory has priority over the value from the local laboratory. Thereafter, additional rules may be provided after consultation with the medical monitor to delineate which value will be defined as baseline.

Laboratory test values will be assessed for severity (grade) based on the numerical component of CTCAE v4.03.

#### **9.3.2. Laboratory Value Summaries**

All test results and associated normal ranges from central laboratories will be reported in SI units. Any laboratory test results and associated normal ranges from local laboratories will be converted to SI units.

When there are multiple laboratory nonmissing values for a participant's particular test at a scheduled visit, central laboratory values have higher priority over local laboratory values. If a tie still exists, the laboratory value with the smallest laboratory sequence number will be used in by-visit summaries.

Numeric laboratory values will be summarized descriptively in SI units, and non-numeric test values will be tabulated when necessary. In addition, line graphs will be provided for ALT, AST, hemoglobin, platelet counts, leukocytes, neutrophils, and lymphocytes.

Shift tables will be presented showing change in CTCAE grade from baseline to worst grade postbaseline. Separate summaries for abnormally high and abnormally low laboratory values

will be provided when the laboratory parameter has both high and low grading criteria. The denominator for the percentage calculation will be the number of participants in the baseline category. The number of participants who experienced worsening of laboratory abnormalities will be summarized by maximum postbaseline severity.

### **9.3.3. Potential Hy's Law Events**

Participants with elevated ALT or AST  $> 3 \times$  ULN range and alkaline phosphatase  $< 2 \times$  ULN range accompanied by total bilirubin  $> 2 \times$  ULN range at the same visit will be listed by treatment group.

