5.4.1.1. Dose Modifications

Dose modification guidance for AEs that have been previously observed in subjects receiving INCB050465 or are potential class-effect AEs are provided (see [Table 3](#) and [Table 5](#)). The starting dose and dose reduction levels of INCB050465 are provided (see [Table 4](#)). Individual decisions regarding dose interruption and reduction should be made using clinical judgment and in consultation with the sponsor's medical monitor, taking into account relatedness of the AE to the study treatment and the subject's underlying condition. Adverse events that have a clear alternative explanation or transient (≤ 72 hours) abnormal laboratory values without associated clinically significant signs or symptoms may be exempt from dose reduction guidelines.

Table 3: Guidelines for Interruption and Restarting INCB050465

ADVERSE EVENT	ACTION TAKEN
Chemistry	

 Grade 3 AST and/or ALT ($> 5.0 \times \text{ULN}$). 
Note: In subjects with liver metastasis-related elevations at baseline, contact sponsor to discuss clinical management and possible dose reductions.
	
Step 1: Interrupt INCB050465 and monitor weekly until the toxicity has resolved to \leq Grade 1.
 
Step 2: Restart INCB050465 at next lower dose with medical monitor approval. Monitor as clinically indicated.

Hematology	

 Grade 3 ANC ($< 1.0 \times 10^9/\text{L}$). Grade 2 platelet count (50 to $< 75 \times 10^9/\text{L}$) for subjects who enrolled with platelets $> 100 \times 10^9/\text{L}$. Grade 3 platelet count ($< 50 \times 10^9/\text{L}$) for subjects who enrolled with platelets $\leq 100 \times 10^9/\text{L}$. 	
Step 1: Interrupt INCB050465 up to 14 days until the toxicity has resolved to \leq Grade 1 or pretherapy baseline. For Grade 3 ANC, monitor at least weekly.
 
Step 2: Restart INCB050465 at same dose; monitor as clinically indicated.

 Grade 4 ANC ($< 0.5 \times 10^9/\text{L}$). Grade 3 or Grade 4 febrile neutropenia. Platelet count is Grade 4 ($< 25 \times 10^9/\text{L}$). 	
Step 1: Interrupt INCB050465 up to 14 days until the toxicity has resolved \leq Grade 2. (Monitor at least weekly.)
 
Step 2: Restart INCB050465 at same dose. Monitor as clinically indicated. If reoccurs, restart at next lower dose.

Other toxicities	

 Diarrhea/colitis. 	See Table 5 .

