- Section 9.2.2 was updated to include details of analyses on time to onset of selected TEAEs of special interest. Summaries of longest duration of selected TEAEs of special interest were added to have a better understanding of the safety profile in terms of duration of class-effect AEs as well as AEs influenced by treatment regimens. "Grade 2 or higher" was changed to "Grade 3 or higher" for time to onset summary of rash. This change was made to be consistent with other PI3K inhibitors, which highlighted more severe cutaneous reactions graded as Grade 3 or higher in the labeling. "Herpes simplex virus infection" was changed to "herpes simplex" based on MedDRA coding dictionary

as a broader term. Exfoliative dermatitis was added to the list of TEAEs of special interest.

- Section 9.2.3 was updated to include summary of TEAEs by PT and maximum severity in decreasing order of frequency, summary of longest duration of selected TEAEs of special interest, and additional supporting summaries during the INCB050465 initial QD dosing period and the maintenance dosing period, which will provide supportive data of the safety profile of the maintenance dose. Summary of nonserious of TEAEs by SOC and PT was removed because it will not be used for the clinical study report but will be provided for result disclosure.
- Section 9.3.2 was modified to include ALT and AST in the line graphs as additional supportive analyses for laboratory events of special interest.
- Section 9.3.3 was added to identify potential Hy's law events to better monitor liver toxicity.
- Section 9.3.4 was updated to align with the analysis plan for adverse events of special interest. Summary of worsening of laboratory events of special interest was removed because this is covered by the summary of worsening of laboratory abnormalities.
- Section 9.5 was updated to change the high threshold of QTcF and QTcB interval from 460 to 450 milliseconds for purpose of analysis. This change is to comply with the categories outlined in FDA Guidance for Industry (E14 Clinical Evaluation of QT/QTc Interval Prolongation and Proarrhythmic Potential for Non-Antiarrhythmic Drugs) used to characterize outliers in QTc values.

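### The potential Hy's law listing needs all criteria at one visit, so a participant whose bilirubin first exceeds 2 x ULN after ALT/AST has fallen to 3 x ULN or below is not listed

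*SAP*

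**What the plan says.** SAP Section 9.3.3 defines the screen in one sentence. It covers "Participants with elevated ALT or AST" above 3 x ULN with ALP below 2 x ULN, "accompanied by total bilirubin" above 2 x ULN, and such participants "at the same visit will be listed by treatment group". No look-forward period and no rule based on peak values appears there or elsewhere in either document. SAP Section 11.2 gives the purpose, under Amendment 1: "Section 9.3.3 was added to identify potential Hy's law events to better monitor liver toxicity". The only output built on the rule is Listing 2.8.5 in SAP Appendix A.

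On sampling, the Protocol Synopsis plans "laboratory assessments every 4 weeks through Week 48 and then every 12 weeks thereafter". Protocol Table 7 sets the windows at 3 days either side through Week 48 and 1 week either side afterwards. For Grade 3 ALT or AST (above 5 x ULN), Protocol Table 3 adds: "Interrupt INCB050465 and monitor weekly until the toxicity has resolved" to Grade 1 or lower.

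**The concern.** The rule treats the transaminase and bilirubin elevations as one event only if one visit shows both. A participant can meet the transaminase and ALP limits on one date and the bilirubin limit on a later date without any visit meeting all three. That participant is absent from the only output meant to find such cases.

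What is at stake is how an empty or short listing is read. ALT and AST of at least 5 x ULN are events of special interest in Protocol Section 8.5, and SAP Section 9.3.4 follows ALT and AST increases as laboratory events of special interest. With about 90 participants planned for Cohort 2, one unlisted case can be the difference between reporting none and reporting one.

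**Working it through.** There is no stated figure to reproduce. The check has four parts.

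**1. The rule applied to two sequences** (multiples of ULN invented for illustration; ALP below 2 x ULN throughout).

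| Case | Visit k | Visit k+1 | Listed under 9.3.3? |
|---|---|---|---|
| A | ALT 6, bilirubin 1 | ALT 2, bilirubin 3 | No: neither visit meets all criteria |
| B | ALT 6, bilirubin 1 | ALT 4, bilirubin 3 | Yes: visit k+1 meets all criteria |

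Bilirubin rises after the transaminase peak in both. Only A is missed, because ALT is no longer above 3 x ULN when bilirubin crosses its limit.

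**2. Whether another output recovers case A.**
- Shift tables (SAP 9.3.2): "Shift tables will be presented showing change in CTCAE grade from baseline to worst grade postbaseline". They work one parameter at a time.
- Time to onset (SAP 9.3.4): ALT and AST, each separately; bilirubin is not included.
- Line graphs (SAP 9.3.2): ALT and AST are included, bilirubin is not.
- Listings 2.8.2 and 2.8.4: these hold the chemistry values but apply no Hy's law criterion.

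None joins a transaminase elevation to a later bilirubin elevation.

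**3. How far a look-forward rule must reach.** Inputs are the Table 7 intervals and windows.
- Through Week 48, the longest gap between consecutive scheduled samples is 28 + 3 + 3 = 34 days.
- After Week 48, the nominal gap is 12 x 7 = 84 days, and the shortest gap between consecutive 12-weekly visits is 84 - 7 - 7 = 70 days.

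A 30-day window can therefore miss the next scheduled sample before Week 48 (34 > 30) and cannot reach it between 12-weekly visits (70 > 30). The weekly checks in Table 3 do not close this gap. They apply only above 5 x ULN and stop at Grade 1 or lower, so a later bilirubin rise falls back on the ordinary schedule.

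**4. Size.** The documents do not say how long either elevation lasts or how far apart they occur. As a labelled assumption, suppose both tests stay above their limits together for d days and only scheduled visits are sampled. The chance that a visit falls in the overlap is min(1, d / interval).

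| Assumed d | 28-day interval | 84-day interval |
|---|---|---|
| 0 days | 0% | 0% |
| 7 days | 7/28 = 25% | 7/84 = 8% |
| 14 days | 14/28 = 50% | 14/84 = 17% |
| 28 days | 28/28 = 100% | 28/84 = 33% |

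The result runs from 0% to 100% depending on d, so it supports no estimate of the share missed. Nor would every miss be recovered by a new rule: if no sample falls within one of the two elevations, no listing can find the case.

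**The case against.** The strongest opposing case is that a same-visit screen is clear, reproducible and contradicts nothing in either document, and that little rests on it. The listing is descriptive, and no endpoint or stated decision depends on it. The values of a missed case stay in the chemistry listings, and manual review is feasible with about 90 participants. Table 3 requires medical monitor approval before restart after Grade 3 ALT or AST, and the IDMC reviews safety data. Protocol Section 1.3 reports no liver test abnormality above Grade 1 on treatment among 72 subjects at doses up to 45 mg QD, so few candidates should be expected. The documents also do not say that bilirubin lags behind transaminases with this drug.

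All of this stands as an argument about importance, and it keeps the point minor. It does not answer the gap itself: none of those safeguards labels a sequential case as a potential Hy's law event, which is the stated purpose of the section. When few cases are expected, the rule that decides whether the listing is empty matters more.

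Three stronger readings are tempting and are not supported.
- A reader might infer that every bilirubin rise after the transaminase peak is missed. Case B shows otherwise.
- A reader might infer that unscheduled samples are excluded. Section 9.3.3 refers to a visit without limiting it to scheduled ones, and Protocol Section 7.5.7 includes unscheduled visits in the central laboratory testing.
- A reader might infer that a known fraction of cases is lost. Any such percentage depends on durations and lags that the documents do not give.

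**Conclusion.** The point holds in a limited form. Following SAP Section 9.3.3 exactly leaves a participant off the only Hy's law output when bilirubin first exceeds 2 x ULN after ALT and AST have fallen to 3 x ULN or below, so that no visit meets all criteria. This follows from the wording of the rule and the list of planned outputs and needs no assumption about the drug.

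How often it would happen cannot be derived. The Phase 1/2 experience suggests rarely. The effect is confined to the sensitivity of one safety listing; efficacy, sample size and error rates are untouched. It is a worthwhile, low-cost improvement and not a defect that threatens the trial's conclusions.

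**What to change.** Keep the same-visit listing and extend Listing 2.8.5 in one of two ways.

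- **Look-forward rule.** Add any participant with treatment-emergent ALT or AST above 3 x ULN, with ALP below 2 x ULN at that sample, and total bilirubin above 2 x ULN on the same day or at any later sample up to and including the next scheduled chemistry visit. State that scheduled and unscheduled samples both count, so that the wording leaves no doubt.
- **Peak rule.** Plot or list peak ALT or AST against peak total bilirubin over the treatment-emergent period.

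Either way, show the sample dates and the days between the two elevations, so that a medical reviewer can discount pairs too far apart to be related. Tying the window to the next scheduled chemistry visit avoids the shortfall of a fixed 30-day window.

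The cost is a sentence or two in Section 9.3.3 and a revised shell for Listing 2.8.5. Both analytes are already in the chemistry panel (Protocol Table 8), so no new data are needed. The downside is a few more cases for medical review. Some will be benign: Protocol Section 3.1 admits participants with Gilbert's syndrome, and with 84 days between visits some pairs will be unrelated. This changes an analysis definition only; it alters no dosing or monitoring rule.
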